9.4.4 Guidelines for significant QTc prolongation

Significant QTc prolongation is defined as an interval > 500 ms or an interval which increases by 60 ms over baseline.

If the prolongation is confirmed on 2 out of the 3 ECGs by either criteria (i.e., QTc interval > 500 ms or > 60 ms increase from baseline) treatment with Debio 1347 should be stopped and the following actions will be taken:

- The patient will be withdrawn from Debio 1347 treatment.
- The patient will be monitored, treated appropriately, and closely followed (ECGs at least three times per week) until the QT and QTc interval return to within 30 ms of baseline.

If an ECG shows significant QTc prolongation the patient should be referred to a cardiologist.

9.5 Subject replacement strategy

- Patients not eligible for the MTD/RP2D determination of the phase 1b portion will be replaced (see section 12.3.3)
- Patients not eligible for efficacy evaluation for the Phase II portion of the study will also be replaced

10.1 EVALUATION DURING TREATMENT/INTERVENTION

	Screening	Treatment							EOT	F/U ^a
Cycle		1				2		3+		Every 12 weeks
Day	-28 to -1	1	4	8	15	28	1	15	1	
		±2	±1	±2	±2	-4	±3	±3	±3	±7
										±14
Written Informed Consent	X									
Review of Eligibility Criteria	X									
Demographic Information	X									
Vital Signs, ECOG PS ^b	X	X			X		X	X	X	X
Height	X									
Physical Exam and Weight	X	X			X		X	X	X	X
12-lead ECG ^c	X	X				X			X	X
ECHO ^c	X								X	X
Haematology and Chemistry blood work ^d	X	X		X	X		X	X	X	X
Tumor markers (CEA and CA15-3)	X	X					X		X	X
Other Bloodwork (CRP LDH, uric acid and γGTP)	X	X		X	X		X	X	X	X
Phosphate (P)			X							
Blood coagulation (PT (INR), APTT)	X	X					X		X	X
Urinalysis ^e	X	X		X	X		X	X	X	X
Calcium regulating hormones bloodwork ^f	X	X					X		X	X
Serum pregnancy test	X									X
Ophthalmological testing ^g	X									X
Adverse events		X		X	X	X	X	X	X	

Fulvestrant		X			X	X			X		
Tumour assessment^h	X								X	X	
Plasma sample for CfDNAⁱ		X			X				X	X	
Pharmacokinetics^j		X			X		X		X		
Tumor Biopsy^k	X										
HepBsAg, HepBcAb, HIV and hepatitis C antibody^l	X										

Abbreviations: DEXA, dual-energy X-ray absorptiometry; ECHO, echocardiogram; ECOG, Eastern Cooperative Oncology Group; EOS, end-of-study; EOT, end-of-treatment (any study treatment); IV, intravenous; PS, performance status.

- a) Survival and disease status will be assessed every 12 weeks (+/- 14 days) until death, withdrawal of consent, or end of the study, whichever is first. Assessments can be collected through phone call or review of patient records.
- b) Blood pressure and heart rate to be collected. BP and pulse rate to be taken after at least 5 minutes of supine rest.
- c) ECG recorded every 3RD cycle *after* Cycle 3. If an ECG shows QTc prolongation (> 470 msec.), the ECG must be repeated twice additionally to obtain values in triplicate. ECHO will be done at baseline, every 3 cycles and at EOT during the phase 1 portion of the study.
- d) Haematology: red blood cells, haemoglobin, hematocrit, platelet count, white blood cells, neutrophils, lymphocytes, monocytes, eosinophils, basophils.
- Blood chemistry(Fasting): total protein, albumin, total bilirubin, AST, ALT, LDH, ALP, γ GTP, CK, total cholesterol, sodium (Na), potassium (K), calcium (Ca), chloride (Cl), phosphate (P), magnesium (Mg), creatinine, BUN, CRP, uric acid, glucose.
- e) Urinalysis: protein, blood, glucose, urobilinogen, pH, sediment, creatinine, calcium (Ca), phosphate (P).
- f) Calcium regulating hormone assessments (whole-PTH, 1,25(OH) 2D, PTHrP) will be performed every cycle until Cycle 3 and every 3 cycles thereafter.
- g) Ophthalmological tests to be repeated as clinically indicated during treatment. Complete ophthalmologic examinations will be performed at screening and, as soon as clinically indicated, if a patient reports any visual abnormality. Complete ophthalmologic examination will be performed and interpreted by a qualified ophthalmologist, including visual acuity testing, slit-lamp ophthalmoscopy and indirect ophthalmoscopy. At the final visit and 28 days after the last dose, slit-lamp ophthalmoscopy will be performed.
- h) Tumor assessments (patients with a history of brain mets will be required to have brain CT scans with contrast or MRIs) to be performed every 8 weeks for 48 weeks (i.e. cycle 2, 4, 6 between days 22 and 28) and then every 12 weeks thereafter (i.e. cycle 9, 12, 15 again between days 22 and 28 etc.).
- i) Plasma samples for cfDNA analysis will be collected prior to dosing on cycle 1, cycle 1 day 15, day 1 of C3 and then at EOT.
- j) Plasma samples for PK will be collected both during phase 1 and 2. Phase 1 PK will be collected prior to dosing on day 1 and 15 of cycle 1 and then day 1 of each cycle thereafter. Phase 2 PK will be collected prior to dosing on day 15 of cycle 1 and day 1 of cycle 2.

k) Baseline tumor biopsies will be obtained during screening for all patients enrolled in the study, at least three fragments on a core biopsy

l) Documented negative tests prior to screening period is acceptable.

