The genotoxic potential of Debio 1347 was assessed in several in vitro and in vivo tests: no mutagenic potential was observed in the Ames test and no increases in structural chromosome aberrations or in polyploid cells were observed in a chromosomal aberration test using human peripheral blood lymphocytes. In an in vivo micronucleus test in rats, however, the numbers of micronucleated immature erythrocytes were slightly increased, suggesting a micronucleus-inducing potential. In vitro, the principal mechanism of micronucleus induction seems not to be due to abnormal chromosome segregation. Based on these results, Debio 1347 is thought to be genotoxic to mammalian cells. Debio 1347 may have an in vivo phototoxic risk based on 1) an in vitro phototoxicity test using a fibroblast cell line, where the compound was suggested as a phototoxic substance (absorbance wavelengths of 200 nm to 400 nm); 2) a whole-body autoradiography in rats after single oral dose of 1 mg/kg of [14C] Debio 1347 suggesting a slower elimination rate of Debio 1347 from skin compared with blood. Although any reproductive and developmental toxicity studies of Debio 1347 have not been conducted, some changes in reproductive organs, such as thinning of vaginal mucosal epithelium and atrophic changes in testes, epididymides, prostate gland, seminal vesicles and uterus were observed at lethal dose in preliminary dose-repeated toxicity in rats. From the above findings and those on bone and cartilage, it is inferred that Debio 1347 may affect reproduction and development.

In the safety pharmacology studies, no effects on the central nervous system or respiratory system were seen in rats at Debio 1347 doses up to 100 mg/kg. Debio 1347 was a potent hERG inhibitor in vitro (IC50: 677ng/mL). However, in the monkey telemetry study, Debio 1347 did not modify the blood pressure, heart rate, and ECG or body temperature at doses up to 10 mg/kg.

No carcinogenicity studies or local tolerance studies have been conducted to date.

Please refer to the Investigator's Drug Brochure for more information.

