6.1 CRITERIA FOR SUBJECT ELIGIBILITY

6.2 Subject Inclusion Criteria

- Males and Females, Age > 18 years
- Written informed consent and authorization obtained from the subject/HIPAA-appointed legal representative prior to performing any protocol-related procedures including screening evaluations.
- Patients with metastatic histologically or cytologically confirmed invasive breast cancer.
- Female patients of postmenopausal status
Postmenopausal status will be defined as following:
 - Age \geq 60 years
 - Age < 60 years and 12 months of amenorrhea plus follicle stimulating hormone and plasma estradiol levels within postmenopausal range by local laboratory assessment in the absence of oral contraceptive pills, hormone replacement therapy, or gonadotropin-releasing hormone (GnRH) agonist or antagonist
 - Prior bilateral oophorectomy
- Pre or perimenopausal women allowed with the addition of goserelin.
- ECOG performance status 0 -1
- Tumor must be estrogen receptor and/or progesterone receptor positive (i.e. Hormone receptor positive (HR+) and HER-2 negative as defined by the ASCO-CAP guidelines: HR+ is defined as expression of ER and/PR in \geq 1% of cells, or HR+ by local laboratory or regional definition. HER2- is defined as a HER2 IHC score of 0 or 1+, or an IHC score of 2+ accompanied by a negative fluorescence, chromogenic, or silver in situ hybridization test indicating the absence of HER2 gene amplification, or a HER2/CEP17 ratio of < 2.0, or local clinical guidelines.

- Tumors must have FGFR amplifications as determined by a CLIA certified laboratory. Patients with FGFR amplifications co-occurring with 11q amplification (CCND1, FGF3,4, 19 amplifications) are also eligible.
- Measurable or evaluable disease per RECIST1.1 or pure lytic or mixed lytic-blastic bone lesions
- No more than 1 prior chemotherapy regimen in the metastatic setting for the phase 2 portion. Patients in the phase 1 portion could have received any number of prior lines of therapy.
- Willing to undergo a new core or excisional biopsy from a metastatic, not previously irradiated tumor lesion during screening
- Life expectancy of greater than 3 months
- Archival Tumor (up to 10 unstained slides) will be obtained, whenever available for additional biomarker analyses
- Hematologic parameters:
 - White blood cell (WBC) count of > 3000/ μ l
 - Absolute neutrophil count (ANC) > 1000/ μ l
 - Platelets > 100,000/ μ l, hemoglobin > 9.0 g/dl
- Non-hematologic parameters:

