10.1 Follow up visits

The mandatory End of Treatment Visit should be conducted approximately 2-4 weeks after the last dose of trial treatment or before the initiation of a new anti-cancer treatment, whichever comes first. All AEs that occur prior to the End of Treatment Visit should be recorded. Subjects with an AE of Grade > 1 will be followed until the resolution of the AE to Grade 0-1 or until the beginning of a new anti-neoplastic therapy, whichever occurs first. SAEs that occur within 30 days of the end of treatment or before initiation of a new anti-cancer treatment should also be followed and recorded.

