10.1.3 End-of-Treatment Criteria

Treatment with Debio 1347 will continue until any of the following occur:

- Patient withdraws consent.
- Disease progression documented by CT scan, physical exam or other objective method of measurement. An exception could be made for patients who progressed due to brain metastases; patients may continue treatment with Debio 1347 if, in the Investigator's opinion, there was reasonable evidence of ongoing clinical benefit.
- Unacceptable toxicity.
- Pregnancy.
- Patient's interests as judged by the Investigator.
- In the event of a Debiopharm International SA decision to no longer supply study drug, ample notification will be provided so that appropriate adjustments to subject treatment can be made.

Patients who are removed from study treatment due to AEs are to be treated and followed-up according to accepted medical practice. All pertinent information concerning the outcome of such treatment will be recorded.

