13.1 CRITERIA FOR REMOVAL FROM STUDY

Subjects may withdraw consent at any time for any reason or be dropped from the trial at the discretion of the investigator should any untoward effect occur. In addition, a subject may be withdrawn by the investigator if enrollment into the trial is inappropriate, the trial plan is violated, or for administrative and/or other safety reasons.

A subject must be discontinued from the trial for any of the following reasons:

- The subject or legal representative (such as a parent or legal guardian) withdraws consent.
- Confirmed radiographic disease progression

Note: A subject may continue on treatment with confirmed radiographic progression if clinically stable or clinically improved.

- Unacceptable adverse experiences
- Intercurrent illness that prevents further administration of treatment
- Investigator's decision to withdraw the subject
- Subject death
- The subject has a confirmed positive serum pregnancy test
- Noncompliance with trial treatment or procedure requirements
- The subject is lost to follow-up

After the end of treatment, each subject will be followed for 30 days for adverse event monitoring (serious adverse events will be collected for 90 days after the end of treatment).

Subjects who discontinue for reasons other than progressive disease will have post-treatment follow-up for disease status until disease progression, initiating a non-study cancer treatment, withdrawing consent or becoming lost to follow-up, for up to 2 years. After documented disease progression, each subject will be followed by telephone for overall survival until death, withdrawal of consent, the end of the study, or 2 years, whichever occurs first.

If consent is withdrawn, the subject will not receive any further investigational product or further study observation.

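### No pregnancy test is scheduled between the first and last dose of Debio 1347, so the pregnancy stopping rules have no scheduled trigger during treatment

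*Combined protocol and SAP*

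**What the plan says.** **Who can enter.** Section 6.2 states: "Pre or perimenopausal women allowed with the addition of goserelin". Women of childbearing potential need a negative urine or serum test in the 72 hours before first dose. Section 6.3 requires contraception during the study and for 6 months after Debio 1347, and does not accept an oral or injectable agent as the only method.

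**The hazard.** Section 3.3.3 concludes that "Debio 1347 is thought to be genotoxic to mammalian cells" and that "it is inferred that Debio 1347 may affect reproduction and development". It also gives reassuring results: "no mutagenic potential was observed in the Ames test", the chromosomal aberration test was negative, and the rat micronucleus increase was slight. Reproductive-organ changes in rats were seen at a lethal dose. No reproductive or developmental toxicity studies have been done.

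**Stopping rules.** Section 10.1.3 begins "Treatment with Debio 1347 will continue until any of the following occur", and pregnancy is on the list. Section 13.1 includes among the mandatory reasons for discontinuation: "The subject has a confirmed positive serum pregnancy test".

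**Testing.** In the section 10.1 schedule the row "Serum pregnancy test" is marked at Screening and EOT only. Section 8.1 lists a test before treatment. On EOT timing, the follow-up section says: "The mandatory End of Treatment Visit should be conducted approximately 2-4 weeks after the last dose of trial treatment", or ahead of a new anti-cancer therapy if that is sooner.

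**The concern.** The plan treats pregnancy as a reason to stop Debio 1347 but schedules no test that could find it during daily dosing. A site that follows the schedule exactly tests a woman before her first dose and again after her last. If contraception fails in between, fetal exposure continues until someone suspects pregnancy or treatment ends for another reason.

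This is a participant-safety point. It has no bearing on the clinical benefit endpoint, the two-stage design, its power or its type I error.

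**Working it through.** The plan states no figure to reproduce. The check is a reading of the schedule followed by simple date arithmetic.

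**1. Reading the row.** The schedule has one Screening column, eight treatment columns (Cycle 1 Days 1, 4, 8, 15 and 28; Cycle 2 Days 1 and 15; Day 1 of Cycle 3 onward), then EOT and follow-up. The pregnancy row has a mark in the first column and the tenth. Because the table was recovered from a PDF, the column positions need confirming. The cell-free DNA row, read the same way, falls on Cycle 1 Day 1, Cycle 1 Day 15, Cycle 3 Day 1 and EOT, as footnote i says. The tenth column is therefore EOT, and the pregnancy row has 0 marks in the eight treatment columns.

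**2. Other places a test could be required.** Sections 6.2, 6.3 and 8.1 all place the test before treatment. No schedule footnote mentions pregnancy testing.

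**3. On-drug time without a scheduled test.** The inputs are the 28-day cycle (section 4.2) and the ±3-day window on Day 1 visits from Cycle 2 (schedule). The current stretch is cycles × 28. With a test on Day 1 of each cycle from Cycle 2, the stretch is 28 days, or 28 + 3 + 3 = 34 at the window limits. Tests added = cycles − 1.

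| Time on Debio 1347 | Now (days) | With Day 1 testing (days) | Tests added |
|---|---|---|---|
| 8 weeks (2 cycles) | 2 × 28 = 56 | 28 (34) | 1 |
| 24 weeks (6 cycles) | 6 × 28 = 168 | 28 (34) | 5 |
| 48 weeks (12 cycles) | 12 × 28 = 336 | 28 (34) | 11 |

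**4. Calendar gap between tests at 24 weeks.** If EOT falls 2 to 4 weeks after the last dose, the gap runs from 168 + 14 = 182 days to 168 + 28 + 3 = 199 days, the 3 being the 72-hour allowance before first dose. These are not firm limits. EOT moves earlier if new therapy starts, and the schedule allows it ±7 days. It could fall later relative to Debio 1347 if fulvestrant continues alone after toxicity, which section 9.4 permits. The on-drug figures in step 3 are the safer measure.

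**5. Feasibility.** Haematology, chemistry and urinalysis are already marked at Cycle 2 Day 1 and at Day 1 from Cycle 3, so a per-cycle test needs no new visit or sample collection.

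**The case against.** **Nothing in the plan is contradictory.** Sections 10.1.3 and 13.1 say what follows once pregnancy is known; they do not say that only a scheduled test may establish it. Physical examinations and adverse-event review recur throughout treatment, and an investigator can order a test at any of them. This stands. A reader might infer that pregnancy cannot be detected on treatment, but the documents support only the narrower statement that no *scheduled* test can detect it. Suspicion is also a weak safeguard here. Absent periods tell the site little in a woman on goserelin, and nausea and fatigue were each reported by 40% of patients in the phase 1 trial (section 3.3.4).

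**Prevention is substantial.** The pre-dose test, contraception throughout, the limit on oral and injectable methods, and goserelin for every pre- or perimenopausal woman together make pregnancy unlikely. This also stands and keeps the point in proportion. But prevention does not detect its own failure, and the protocol lists pregnancy as a stopping event, so it does not treat failure as impossible.

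**The size is not shown.** This stands as well. The documents give neither the number of women of childbearing potential nor a contraceptive failure rate. A reader might multiply the design rates of 10% and 25% by 43 and infer that 4 to 11 patients face long exposure. The documents do not support that. It assumes full accrual, although at a true rate of 10% the design stops at 18 patients with probability 0.73. It also treats clinical benefit as time on drug, although a response counts without a stated minimum duration. And it covers all patients, not women of childbearing potential.

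**Conclusion.** The gap is real and worth closing as a low-cost safety improvement. Between first and last dose the number of scheduled pregnancy tests is 0, so on-drug time without one equals the whole treatment: 168 days at 24 weeks, against about 28 (34 at window limits) with per-cycle testing.

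The conclusion rests on the schedule row, confirmed by the cell-free DNA footnote, and on EOT following the last dose. Monthly testing is a judgement, chosen because it fits collections already made; a test every third cycle would leave 3 × 28 = 84 on-drug days.

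The affected group is an unknown part of at most 43 phase 2 patients plus replacements (section 9.5), since section 9.2.1 says the phase 1 patients were already off study. A reader might infer a quantified fetal risk or an established human hazard. Neither follows: no failure rate is given, and the genotoxicity evidence in section 3.3.3 is mixed.

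**What to change.** Leave in place the serum tests at Screening and EOT and the test within 72 hours before first dose. In the same schedule row, add marks for women of childbearing potential at Cycle 2 Day 1 and at Day 1 of every later cycle. Use serum from the blood already drawn, or urine with serum confirmation if the result is positive or unclear; section 6.2 already uses that confirmation step. Hold Debio 1347 until a positive or unclear result is resolved, and handle a confirmed positive under sections 10.1.3 and 13.1.

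The hold should cover Debio 1347 only. The reproductive-risk evidence in section 3.3.3 concerns that drug, and section 11.2 gives no such finding for fulvestrant.

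The cost is a change to one schedule row, one inexpensive assay per cycle for the women concerned (5 added tests over 24 weeks), and an occasional short interruption of Debio 1347 for a false positive.

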3.3.4. Clinical data

Based on these data a phase 1 first –in-human trial was undertaken, and it has now completed the patients' enrollment in the dose-escalation portion.

A total of 57 patients with genetically activated advanced solid tumours were included into the dose-escalation part up to 06 April 2017. All had received at least one dose of Debio 1347 and were assessable for safety. Of these, 54 were evaluable for efficacy. Eight dose levels had been tested at the time of cut-off (10, 20, 30, 40, 60, 80, 110 and 150 mg daily).

The MTD is 80mg since 2 DLTs were observed at 110 mg daily. Five patients experienced DLTs: NCI-CTCAE Grade 2 intolerable dry mouth and dry eyes at 60 mg, Grade 3 hypercalcaemia and Grade 3 hyperamylasaemia both at 80 mg, and Grade 3 bilirubin increase and Grade 3 hyperphosphatemia and Grade 3 stomatitis in two patients at 110 mg,

respectively. At cut-off, treatment emergent adverse events (TEAEs) had been reported by all patients. At data cut-off, the most common treatment-emergent adverse events (TEAE) were hyperphosphatemia (75%), fatigue (40%), diarrhea (39%), nausea (40%), and inappetence (32%). Eighteen patients (32%) experienced a grade ≥ 3 related TEAE. Twenty-eight patients (49%) required dose modification, primarily due to hyperphosphatemia and cutaneous toxicity.

Decreased left ventricular ejection fraction (LVEF) was reported in 1 patient (Grade 2) and 2 patients experienced respectively non-clinically significant Grade 1 and 2 ECG QTc prolongation.

Clinical activity started at the dose of 30 mg. Five patients had a partial response (PR): an endometrial cancer patient with FGFR1 amplification (30 mg), a cervical cancer patient with FGFR2 mutation (80 mg), an urothelial cancer harbouring a FGFR3-TACC3 translocation (80 mg), a cholangiocarcinoma patient with FGFR2 mutation (110 mg), and a colon cancer patient with FGFR2 fusion (110 mg) and an urothelial cancer with FGFR3 harbouring a FGFR3-TACC3 translocation (150 mg). An additional 10 patients had target regression $< 30\%$. Two out of these patients had a breast cancer. A triple-negative breast cancer patient with FGFR1 amplification showed a reduction in the target lesions of 19% (40 mg), while a HR+ Her2+ breast cancer patient with FGFR1 amplification showed a reduction in the target lesion of 12% (60 mg).

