6.3 Subject Exclusion Criteria

- Prior Fulvestrant for metastatic breast cancer will be allowed for phase 1 portion but not for the phase 2 portion
- History of hypersensitivity to any of the excipients in the Debio 1347 formulation (lactose hydrate, microcrystalline cellulose, croscarmellose sodium, hydroxypropyl cellulose, sodium lauryl sulfate, and magnesium stearate).
- Other malignancies requiring active treatment in the last 6 months.
- Brain tumors and/or brain metastases unless they are asymptomatic, stable on recent imaging (not dated more than 30 days from the inclusion date) and have not required active treatment in the last 6 months.
- History and/or current evidence of endocrine alteration of calcium-phosphate homeostasis.
- History of myocardial infarction or stroke within 6 months, congestive heart failure greater than NYHA class II, unstable angina pectoris, unexplained recurrent syncope, cardiac arrhythmia requiring treatment or family history of sudden death from cardiac-related causes.
- Baseline Frederica’s corrected QT (QTcF) interval greater than 470 msec (female) or greater than 450 msec (male), history of congenital long QT syndrome, the presence in the screening ECG of a conduction abnormality that in the opinion of the Investigator would preclude safe participation in this study.
- Concomitant use of a drug with a known risk of QTc prolongation
- Current anticoagulation therapy with therapeutic doses of warfarin (low-dose warfarin \leq 1mg/day or low molecular-weight heparin are permitted).
- History and or current evidence of ectopic mineralisation/calcification including but not limited to the soft tissue, kidneys, intestine, myocardium and lung with the exception of calcified lymph nodes and asymptomatic coronary calcification.

- Concomitant use of high dose systemic steroids and other drugs such as calcitonin preparations, active Vitamin D3 preparations, estrogen preparations, selective estrogen receptor modulators, Vitamin K2 preparations, parathyroid hormones, phosphorus absorbers. Note, inhaled, topical steroids and low tapering doses of steroid especially in patients treated recently for brain metastases will be included.
- Corneal disease, such as bullous or band keratopathy, corneal desquamation, keratitis, corneal ulcer, or keratoconjunctivitis.
- Known infection requiring the systemic use of, for example, an antibiotic or antiviral agent.
- Known HIV, HBV or HCV infection.

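### Triplicate ECGs are required only above 470 ms, so a QTc rise of more than 60 ms ending at or below 470 ms has no required confirmation for the stopping rule

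*Combined protocol and SAP*

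**What the plan says.** Section 9.4.4 gives the definition: "Significant QTc prolongation is defined as an interval > 500 ms or an interval which increases by 60 ms over baseline". The stopping rule follows: "If the prolongation is confirmed on 2 out of the 3 ECGs by either criteria (i.e., QTc interval > 500 ms or > 60 ms" above baseline, Debio 1347 is stopped, the patient is withdrawn from it, and ECGs are taken at least three times a week until the interval is back near baseline. The section does not say when the second and third ECGs are to be taken. Its last sentence acts on one tracing: "If an ECG shows significant QTc prolongation the patient should be referred to a cardiologist".

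The instruction to take three ECGs is in the schedule of section 10.1, footnote c: "If an ECG shows QTc prolongation (> 470 msec.), the ECG must be repeated twice additionally to obtain values in triplicate". It uses an absolute value only. The schedule places ECGs at screening, Cycle 1 Day 1, Cycle 1 Day 28, Cycle 3 Day 1 and end of treatment. Footnote c adds one every third cycle after Cycle 3.

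Section 6.3 excludes a baseline QTcF "interval greater than 470 msec (female) or greater than 450 msec (male"). It sets no lower limit.

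**The concern.** The stopping rule has two criteria, but the step that produces the ECGs needed to apply it is tied to neither. An absolute trigger of 470 ms lies below 500 ms, so it catches every value relevant to the first criterion. It does not track change from baseline, so it catches the second criterion only when the value also exceeds 470 ms.

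If the schedule is followed as written, a patient can meet the definition of significant prolongation with no repeat ECG required. Without a repeat, the two-of-three condition cannot be met, so neither the withdrawal nor the intensified ECG follow-up that depends on it is reached. Two patients with the same rise can then be treated differently because they started from different baselines.

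QTc is a reasonable thing to watch with this drug. Section 3.3.3 describes potent hERG inhibition in vitro (IC50 677 ng/mL), and section 11.1 lists QTc prolongation, hypokalemia and hypomagnesemia among expected effects. Section 6.3 excludes drugs with a known QTc risk at entry, but section 9.1.2 asks only for caution with them on study.

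**Working it through.** The plan states no figure to reproduce here. The check is threshold arithmetic, followed by a sensitivity range for how often the gap would matter.

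**Inputs from the documents**
- Repeat-ECG trigger: QTc > 470 ms (10.1, footnote c).
- Stopping criteria: QTc > 500 ms, or a rise > 60 ms, on two of three ECGs (9.4.4).
- Baseline QTcF: at most 470 ms (women) or 450 ms (men), with no lower limit (6.3).
- Cycle length 28 days; at most 43 phase 2 patients (14.0).

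**Step 1: the 500 ms criterion.** Any value above 500 is above 470, so triplicates are always required. No gap.

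**Step 2: the 60 ms criterion.** Let b be the baseline and q the on-treatment value. The gap is q − b > 60 with q ≤ 470. It is non-empty only if b + 60 < 470, that is b < 410. Its width is 470 − (b + 60) = 410 − b.

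| Baseline (ms) | Rises with no required repeat | Width (ms) |
|---|---|---|
| 380 | > 60 to 90 | 30 |
| 390 | > 60 to 80 | 20 |
| 400 | > 60 to 70 | 10 |
| 405 | > 60 to 65 | 5 |
| 410 or more | none | 0 |

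A 1-ms grid over eligible baselines gives 409 ms as the highest baseline in the gap for both sexes. If the definition is read as a rise of 60 ms or more, the bound moves to 410 ms.

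**Step 3: worked pair.** Baseline 390 ms, Cycle 1 Day 28 value 455 ms: a rise of 65 ms, no required repeat. Baseline 415 ms with the same rise reaches 480 ms: triplicates are required, and the patient is withdrawn if a second tracing agrees. In the first case the next scheduled ECG is Cycle 3 Day 1, about four weeks later. After Cycle 3 the interval is 3 × 28 = 84 days.

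**Step 4: how often.** The documents give no QTc distributions, so these are assumptions. Baseline is normal with mean 400, 410, 420 or 430 ms and SD 15 or 20, truncated at 470. The on-treatment change is independent and normal with mean 0, 10, 20 or 30 ms and SD 15 or 20. That makes 64 combinations. For each,

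P(gap) = ∫ over b < 410 of f(b) × P(60 < change ≤ 470 − b) db.

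- P(gap) per ECG: 0.000002 to 0.036, median 0.0011.
- Times 43 patients: 0.0001 to 1.55 per scheduled ECG; at the median, 43 × 0.0011 ≈ 0.05.
- Share of all rises > 60 ms that fall in the gap, by baseline mean: 400 ms, 53–67%; 410 ms, 31–43%; 420 ms, 13–26%; 430 ms, 4–13%.

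**Step 5: after the change.** With a trigger of > 470 ms or a rise > 60 ms, every value meeting either stopping criterion triggers repeats, so the gap is empty.

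**The case against.** The strongest reply is that section 9.4.4 closes the gap itself. A rule tested on three ECGs for either criterion presupposes that three are taken for either criterion, and footnote c could be an additional, more sensitive repeat rule rather than a limit. The wording allows that reading, and nothing forbids a repeat. But it presumes the tracings without ordering them, and staff working from the schedule will find one explicit trigger, at 470 ms.

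Second, a single qualifying ECG already leads to cardiology referral. That stands: the four-week and 84-day intervals are gaps between scheduled ECGs, not periods without action. The referral, however, has no stated timing, does not require a repeat ECG or a dose hold, and does not operate the stopping rule.

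Third, the values concerned are not extreme. All are at or below 470 ms, a level at which a woman may enter the trial. The male limit is 450 ms, so this does not cover every male case. The drug's record is also fairly reassuring: in the first-in-human study "2 patients experienced respectively non-clinically significant Grade 1 and 2 ECG QTc prolongation", among 57 patients, and "in the monkey telemetry study, Debio 1347 did not modify the blood pressure, heart rate, and ECG" at doses up to 10 mg/kg.

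Fourth, the upper end of the frequency range is a corner case (baseline mean 400 ms with SD 15, mean change +30 ms with SD 20). It implies a 6.7% chance of a rise above 60 ms on each ECG, or 0.067 × 57 ≈ 3.8 patients on a single ECG in a group the size of the first-in-human study. Two QTc cases of any kind were reported there, though lower doses were included. Nothing in the documents supports a +30 ms mean shift, so the median is the fairer guide. Section 9.2.1 also says the phase 1 patients are off study, so only phase 2 is exposed.

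**Conclusion.** The concern holds. As written, a rise of more than 60 ms ending at or below 470 ms meets a stopping criterion for which the protocol requires no confirming ECGs. That follows from the text and simple arithmetic, and applies only to baselines below 410 ms.

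The practical size is small and rests on assumed distributions: most plausibly a small fraction of one patient per scheduled ECG, and about 1.5 of 43 only at the extreme of the range. The share of qualifying rises that escape the trigger could still be material, 13–26% at an assumed baseline mean of 420 ms. Adverse event recording does not depend on confirmation, and efficacy conclusions are untouched. This is a low-weight safety point that should be fixed because a mandatory stop needs a mandatory confirmation step and the remedy is cheap.

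**What to change.** Widen the trigger in footnote c of section 10.1, for example: *Repeat the ECG twice at the same visit whenever QTc is above 470 msec or has risen by more than 60 msec from baseline.* A cross-reference from section 9.4.4 to the footnote would remove any doubt about which three ECGs are meant.

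Three optional clarifications in section 9.4.4: use the same strict inequality in the definition and the stopping rule, state that QTc means QTcF as in section 6.3, and say whether the screening or the Cycle 1 Day 1 ECG is the baseline.

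The cost is one clause, and two extra tracings at the same visit for the few patients whose rise exceeds 60 ms but ends at or below 470 ms. Endpoints, sample size and analysis do not change.
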